## **Observation measures**

### **Validity Index**

#### **Main efficacy measures**

Changes of MADRS score at therapeutic visit point compare with baseline.

#### **Secondary efficacy measures**

1. Changes of QIDS-SR score at therapeutic visit point compare with baseline.
2. Changes of HAMA score at therapeutic visit point compare with baseline.
3. Changes of individual score of MADRS at therapeutic visit point compare with baseline.
4. Changes of YMRS score at therapeutic visit point compare with baseline.

5. Efficacy after 2 and 4 weeks of treatment.(Efficacy means that the score of MADRS decreasing by more than or equal to 50% compares with its baseline score)

[figure not shown]
6. Remission rate after 2 and 4 weeks of treatment.(Remission means that the total score of MADRS is less than 10.)

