## **Introduction**

Depression is one of the most serious mental diseases, bringing great burden to society and families. Currently, antidepressant drugs commonly used in clinic mainly are tricyclic and monoamine substance reuptake inhibitors discovered in the 1950s and 1960s, which are classic monoamine strategy drugs. They improve depressive symptoms by increasing the concentration of monoamine transmitter in the brain, but their onset time is slow and efficacy is low. These drugs are only effective for about 60 - 70% of patients with depression, while the remaining 30% may be patients with treatment-resistant depression. In addition, the onset time is delayed and often takes weeks and months to begin. Some even cause side effects of drugs (such as anxiety) before taking effect, aggravating the suicidal tendency of depressive patients. In recent years, ketamine, as a new antidepressant, has been hailed as the largest discovery in the past half century because of its rapid antidepressant effect (rapid improvement of mood in a few hours) and its efficacy in over 70% of patients with refractory depression. However, ketamine is classified as a psychotropic drug due to its potential addiction, which limits its application in clinical anti-depression treatment.

[name]'s research group applied a variety of research tools of neuroscience, such as behavioral pharmacology, electrophysiology and photogenetics, to elucidate the neurological mechanism of ketamine's rapid antidepressant effect, that was, ketamine blockaded the N-methyl-D-aspartate receptor (NMDAR) and low-voltage-sensitive calcium channel (T-VSCCs)-dependent cluster discharges in the lateral habenular nucleus located in the reward center, which led excessive inhibition of downstream monoamine reward brain regions, and ultimately caused rapid antidepressant effects.

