#### **Exclusion criteria**

1. Diagnoses of other mental disorders (such as organic mental disorders, schizophrenia, bipolar and related disorders, anxiety disorders, obsessive-compulsive disorders and so on) are made according to DSM-V criteria;
2. Depressive episodes, such as depression caused by hypothyroidism, secondary to a systemic disease or an organic mental disorder caused by a neurological disease;

3. Subjects with a history of attempted suicide, or currently at high suicide risk, or with suicide behavior/attempt, or scoring more than or equal to 3 points on the 10th clause of MADRS scale;
4. Subject whose score of MADRS scale in baseline period will be 25% lower than that in screening period;
5. Subjects with a history of severe or poorly controlled cardiovascular, liver, kidney, blood, endocrine, respiratory diseases, etc;
6. Subjects with a history of epileptic seizures, except for a single febrile convulsion in children;
7. Researchers believe that the results of subjects' physical and laboratory examinations are clinically significant abnormalities in screening or baseline period. The following indicators exceed the following criteria: 1)ALT or AST levels are 1.5 times higher than the upper limit of laboratory normal values. 2)Thyroid Function are 1.1 times higher than the upper or lower limit of normal values. 3) Serum creatinine values are 1.1 times higher than the upper limit of normal values. 4)The levels of blood urea nitrogen are higher than the upper limit of normal values;
8. The result of electrocardiogram (ECG) is abnormal in screening or baseline period, such as male subjects with QTc interval ( $> 450$  ms) and female subjects with QTc interval ( $> 470$  ms) , and the researchers thought it is not suitable for selection;
9. Subjects could not swallow oral medicines or have a history of gastrointestinal surgery or any other diseases that may interfere with drug absorption, distribution, metabolism or excretion;
10. Monoamine oxidase inhibitors (MAOIs) are taken by subjects now or within 2 weeks before screening. Subjects who took antipsychotics, antidepressants or mood stabilizers before randomization and these drugs' cleaning phase had less than five half-lives. Subjects who took fluoxetine within 1 month before screening. Subjects who continue to take Chinese medicines with antidepressant effects specified in the instructions after signing informed consent.

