#### **Withdrawal criteria**

Subjects withdrawing from the study: subjects who quit voluntarily and who need to withdraw after medical assessment of researchers.

1. Subjects who break off informed consents at any time;
2. Subjects who are lost to follow-up;
3. Severe adverse events, or intolerable adverse events happen, and are identified by the researchers that subjects need to quit;
4. Subjects who violate the protocol severely that affect the assessment of safety and efficacy of the research definitely;
5. Subjects who get psychiatric symptoms, mania, suicidal or self-injurious behaviors during the study;
6. Subjects who are pregnant during the study;
7. Subjects need to withdraw from the study in other situations after assessment of researchers.

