3.2 Safety Index

Adverse events, Vital signs, Physical examination, Laboratory tests(Including complete blood count, routine urine, blood biochemical examination, prolactin), ECG: 12 leads cardiogram, Scale evaluation.

4. Patient population analysis

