5.4 Clinical Efficacy of Drug Treatment Analysis

The efficacy of drugs will be judged by analyzing the changes from baseline to treatment point in each scale score. Two-way Repeated Measures Anova will be used to compare the efficacy between experimental and control group; intervention measures will be defined as inter-group variables, and time points of scale evaluation as inner-group variables. First, the scale scores of each participant at baseline and each treatment point be listed (Table 2), and the average value of each group will be calculated. Then, values of sum of squares of deviation from mean, degree of freedom and mean square will be calculated. After calculating F values of inter-group factors or inner-group variables, the corresponding P values by querying F value threshold table and statistical inferences will be determined. It should be noted that the degree of freedom of inner-group variables needs to be corrected in the statistical test.

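### MADRS item 10 is scored at every post-baseline visit but analysed only as a mean change in efficacy, so patients whose suicide-risk score emerges on treatment need not be counted by arm

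*Protocol*

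**What the plan says.** **Entry.** Exclusion criterion 3 of the protocol removes "Subjects with a history of attempted suicide, or currently at high suicide risk, or with suicide behavior/attempt", and also anyone "scoring more than or equal to 3 points on the 10th clause of MADRS scale". Whole-number item 10 scores at entry are therefore 0, 1 or 2. The criterion does not state its time point, but eligibility is checked at both Visit 0 and Visit 1.

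**Collection.** The MADRS is scored at Visits 2 to 10 (Days 2, 3, 4, 6, 10, 14, 22, 29 and 42).

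**Analysis.** Protocol, Secondary efficacy measures, no. 3 is "Changes of individual score of MADRS at therapeutic visit point compare with baseline", and SAP 3.1.2 repeats it. I read this as item scores, because the total is already the main measure. SAP 5.4 gives the method: "The efficacy of drugs will be judged by analyzing the changes from baseline to treatment point in each scale score", using group averages and a two-way repeated-measures ANOVA. Item 10 is not named in either place.

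**Safety.** SAP 3.2 begins "Adverse events, Vital signs, Physical examination, Laboratory tests" and goes on to ECG and a scale evaluation. The protocol's Safety Index names that scale as SAFTEE, and SAP 5.5.6 tabulates it. SAP 5.5.1 summarises adverse events overall and by relatedness, seriousness, severity, discontinuation and death. Withdrawal criterion 5 covers "Subjects who get psychiatric symptoms, mania, suicidal or self-injurious behaviors during the study". None of these refers to item 10, a worst post-baseline score or a shift table.

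**The concern.** The protocol's Introduction says that side effects of some existing antidepressants, arising before benefit does, end up "aggravating the suicidal tendency of depressive patients". In this trial prior antidepressants are washed out. One arm takes placebo and the other ethosuximide for two weeks, and both arms then start escitalopram or a substitute antidepressant. Emergent suicidality is therefore a safety question in both phases.

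Item 10 is the repeated measure in the plan that bears on it most directly, yet it is treated as one efficacy item among others and averaged. What matters for safety is how many patients get worse and by how much, and a mean does not show that. The trial could report improvement on the item while a few patients had worsened sharply. Missing values are not imputed (SAP 5.2), so patients who worsen and leave also drop out of the later means.

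**Working it through.** The plan gives no figure for item 10 to reproduce. The check is whether a falling mean can coexist with emergent scores, and on what scale.

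**Inputs**
- n = 20 per arm (SAP 2.2).
- Entry score at most 2 (exclusion criterion 3).
- Assumed: whole-number item scores with a minimum of 0. The documents do not give the item range. They imply that 3 is attainable; examples using 4 or 6 assume that the scale reaches that far.
- Assumed: the baseline values and patterns of change below, which are illustrations and not forecasts.

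**Step 1: one arm.** All 20 start at 1; 18 fall to 0 and 2 rise to 4.

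Mean change = [18 × (-1) + 2 × 3] / 20 = (-18 + 6) / 20 = -0.6.

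Patients newly at 3 or more: 2/20 = 10%.

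**Step 2: how many can worsen unseen.** Let all start at b, k rise to t and the rest fall to 0.

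Mean change = [k(t - b) - (20 - k)b] / 20 = (kt - 20b) / 20.

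This is below zero when k < 20b/t.

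| b | t | 20b/t | largest k | mean change |
|---|---|---|---|---|
| 1 | 3 | 6.67 | 6 | -0.10 |
| 1 | 4 | 5 | 4 | -0.20 |
| 2 | 3 | 13.33 | 13 | -0.05 |
| 2 | 4 | 10 | 9 | -0.20 |

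These are upper bounds, because everyone else is assumed to fall to 0. The rows with t = 3 need no assumption about the top of the scale.

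**Step 3: does the entry criterion cause this?** Take t = 6 (assumed attainable). At b = 2, the highest score allowed, 20b/t = 6.67, so k is at most 6. At b = 3 and b = 4, which the criterion rules out, k is at most 9 and 13. The criterion reduces what a mean can hide. Its useful effect is that any later score of 3 or more is emergent.

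**Step 4: two arms.** SAP 5.4 compares arms, so one arm's mean is not the whole result. Set the arm in step 1 beside an arm that also starts at 1, with 12 falling to 0 and 8 unchanged: mean change = 12 × (-1) / 20 = -0.6. The means are equal, but the counts at 3 or more are 2/20 and 0/20.

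**Step 5: what a count can show with 20 per arm**
- 2 v 0: two-sided Fisher p = 2 × (190/780) = 0.49. For 3 v 0, p = 0.23; for 5 v 0, p = 0.047.
- Chance of at least one case in an arm: 1 - 0.95^20 = 64% at a true rate of 5%, and 1 - 0.90^20 = 88% at 10%.
- If 0/20 are seen, the upper limit of the two-sided 95% interval is 1 - 0.025^(1/20) = 16.8%.

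**The case against.** The best defence is that the plan has other ways to see suicidality, and four points in it deserve weight.

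**Other routes exist.** A reader might infer that the safety plan contains no measure of suicidality, or that no planned output would reveal these patients. The documents support neither. Adverse events are recorded at Visits 1 to 10 and summarised in SAP 5.5.1. SAFTEE is a named and tabulated safety scale, and whether it covers suicidal thoughts cannot be settled from the documents. Withdrawal criterion 5 mentions psychiatric symptoms as well as suicidal behaviour, so it is not confined to behaviour. SAP 5.3.1 lists details of patients who do not complete, and SAP 5.4 lists each participant's scale scores. What remains is narrower. No item 10 score is linked to an adverse event or a withdrawal. The score listing does not say whether it holds item scores, and a listing is not a count by arm. SAFTEE is absent from the contents of every visit, though it may be in the flow chart, which cannot be read in the available copy.

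**The entry criterion is not to blame.** A reader might take the cap below 3 as the source of the masking. Step 3 shows the opposite; averaging is the source, and it would affect any item.

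**The example is constructed, and the ANOVA compares arms.** Both are true. Against an arm in which all 20 fell from 1 to 0 (mean -1), the arm in step 1 would look worse, not better. Step 4 shows that equal means with unequal counts are also possible, so the comparison between arms gives no assurance.

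**A cut-off of 3 is an entry filter.** That is right. Using it after baseline is a reporting choice and gives it no standing as a threshold for action.

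**Conclusion.** The point holds in a limited form. Item 10 is collected nine times after baseline, and its only specified analysis is a secondary efficacy change compared through group means. That analysis can report improvement while patients newly reach 3 or more: a mean change of -0.6 with 2/20 (10%) in the illustration, and up to 6 of 20 reaching 3 under the extreme pattern with a common baseline of 1. Other safety routes may catch some of these patients, but none is guaranteed to count them by arm.

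The conclusion rests on reading individual score as item score, on exclusion criterion 3 being applied up to baseline, and on whole-number scoring. The example in step 1 also needs a scale that reaches at least 4. It does not imply that harm is expected, or that a count would be powered to test for it. The plan should be changed because the data will already exist and the gap is cheap to close.

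**What to change.** In the protocol's Safety Index, SAP 3.2 and SAP 5.5, add a descriptive safety summary of MADRS item 10 on the Safety Set, by arm:

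1. A shift table from baseline score to worst post-baseline score.
2. The number and percentage with any post-baseline score of 3 or more, separately for Days 2-14 (Visits 2 to 7) and Days 22-42 (Visits 8 to 10). The denominator is patients with at least one item 10 score in that period. State that 3 is a reporting cut-off only and not a rule for clinical management.
3. A listing of those patients with their item 10 scores by visit, including anyone later withdrawn.

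Keep the mean change as the secondary efficacy measure, and say in SAP 3.1.2 that individual score means item score. Present the counts without formal testing, with the sample size noted beside them.

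The cost is a few lines of wording, two short tables and one listing, all from data already collected. No visit, instrument or change in patient care is needed.

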### **Safety Index**

1. Adverse events;
2. Vital signs;
3. Physical examination;
4. Laboratory tests(Including complete blood count, routine urine, blood biochemical examination, prolactin);
5. ECG: 12 leads cardiogram;
6. Scale evaluation(SAFTEE).

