3.1.2 Secondary efficacy measures

Changes of Quick Inventory of Depressive Symptomatology – Self Report (QIDS-SR) score at therapeutic visit point compare with baseline.

Changes of Hamilton Anxiety Rating Scale (HAMA) score at therapeutic visit point compare with baseline.

Changes of individual score of MADRS at therapeutic visit point compare with baseline.

Changes of Young Mania Rating Scale (YMRS) score at therapeutic visit point compare with baseline.

Efficacy after 2 and 4 weeks of treatment.(Efficacy means that the score of MADRS decreasing by more than or equal to 50% compares with its baseline score)

Remission rate after 2 and 4 weeks of treatment.(Remission means that the total score of MADRS is less than 10.)

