4.1 Efficacy Set

Efficacy Set contains a set of subjects that meet all the following requirements.

- 1) All patients who are received study drug.
- 2) Patients who have scale scoring data at least at one time point after drug administration.

The Efficacy Set will be used for analysis of the efficacy of drugs.

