5.2 Handling of Missing data

Unless otherwise specified, missing values will not be imputed.

[figure not shown]

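### YMRS is planned only as a mean efficacy change, a comparison likely to miss emergent mania; it should be reported as a safety measure with peak scores and case counts by arm

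*Protocol*

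**What the plan says.** **Role of the scale.** The protocol's Secondary efficacy measures include "Changes of YMRS score at therapeutic visit point compare with baseline". SAP 3.1.2 repeats it: "Changes of Young Mania Rating Scale (YMRS) score at therapeutic visit point compare with baseline". YMRS is scored at baseline and at nine later visits, from Day 2 to Day 42.

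**Population and withdrawal.** The first exclusion criterion covers "Diagnoses of other mental disorders (such as organic mental disorders, schizophrenia, bipolar and related disorders, anxiety disorders" and others. The Withdrawal criteria include "Subjects who get psychiatric symptoms, mania, suicidal or self-injurious behaviors during the study". The visit schedule describes no early-termination visit with scale scoring.

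**Analysis.** SAP 5.4 judges efficacy by change from baseline on each scale: "Two-way Repeated Measures Anova will be used to compare the efficacy between experimental and control group". It describes the classical calculation (sums of squares, mean squares, an F value checked against a table, corrected within-subject degrees of freedom). SAP 5.2 adds: "Unless otherwise specified, missing values will not be imputed". For the Efficacy Set, SAP 4.1 asks for study drug received and "Patients who have scale scoring data at least at one time point after drug administration". SAP 5.1 states intention-to-treat as the main principle.

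**Safety.** The protocol's Safety Index names one scale, "Scale evaluation(SAFTEE"). SAP 3.2 mentions a scale evaluation without naming the scale, and SAP 5.5 has a subsection for SAFTEE but none for YMRS. Neither document sets a YMRS cut-off or plans a count of patients with emergent mania.

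**The concern.** With bipolar disorder excluded, low baseline YMRS scores are plausible. A fall from baseline would then say little about benefit, and the informative movement is a rise in a few patients. The plan summarises that movement in the way least likely to show it, as a group mean compared by ANOVA.

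Two features compound each other. A patient who becomes manic is to be withdrawn, so later scores are likely to be missing, and a classical repeated measures ANOVA without imputation has no place for an incomplete row. And even if the patient is kept, one or two large rises among 20 patients shift the mean little and inflate the variance.

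What is at stake is interpretation. A flat YMRS curve in the efficacy results could be quoted as evidence that the drug does not induce mania, when the comparison had little chance of showing otherwise. No primary conclusion depends on this.

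**Working it through.** The documents give no expected mania rate, YMRS standard deviation, threshold, alpha or power, so there is no stated figure to reproduce. What follows is illustration. The only input from the documents is 20 patients per arm (protocol, Number of subjects; SAP 2.2).

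**1. What the mean shows.** Let k of 20 patients in one arm become manic, each with a YMRS rise of r points (assumed), and none in the other arm. If they are kept and scored, the expected difference in last-visit means is k × r / 20:

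| k | r = 10 | r = 20 | r = 30 |
|---|---|---|---|
| 1 | 0.5 | 1.0 | 1.5 |
| 2 | 1.0 | 2.0 | 3.0 |
| 3 | 1.5 | 3.0 | 4.5 |

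If they are left out as incomplete cases, the expected difference is 0 whatever k and r are. With k = 2, for example, the analysis runs on 20 − 2 = 18 patients, none of them a case.

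**2. How often a test of means would react.** Simulation, 4,000 runs per setting. Assumptions: SD 2, within-patient correlation 0.5, a rise of 20 points from the sixth post-baseline visit, two-sided alpha 0.05. The tests were t-tests on each patient's average over nine post-baseline visits and on the last visit. They stand in for the ANOVA; the group-by-time interaction itself was not simulated.

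| k of 20 | Kept, visit average | Kept, last visit | Removed (either test) |
|---|---|---|---|
| 1 | 4% | 2% | about 5% |
| 2 | 9% | 6% | about 5% |
| 3 | 20% | 20% | about 5% |

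The last column is the false-positive rate. The kept columns are generous, because they assume that manic patients are scored to the end of the study. With one case the rejection rate falls below 5%, since a single extreme value adds more to the variance than to the difference.

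**3. Whether a count would do better.** As a formal test, hardly. For k of 20 against 0 of 20, Fisher's exact two-sided p is 2 × C(20,k) / C(40,k):

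- k = 1: 2 × 20/40 = 1.00
- k = 2: 2 × 190/780 = 0.49
- k = 3: 2 × 1,140/9,880 = 0.23
- k = 4: 2 × 4,845/91,390 = 0.11
- k = 5: 2 × 15,504/658,008 = 0.047

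As a description it does better, because each case stays visible. The chance of at least one case in an arm of 20 is 1 − (1 − p)^20. At an assumed true rate of 5% this is 64%, and at 10% it is 88%.

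**The case against.** The strongest reply is that mania would be seen elsewhere. SAP 5.4 lists every participant's scale scores by time point, so a raised YMRS recorded before withdrawal would appear. SAP 5.3.1 lists patients who do not complete. SAP 5.5.1 summarises adverse events by group, including serious events and those that end treatment. SAP 5.5.6 tabulates SAFTEE, and adverse events are recorded at every visit from baseline. This stands. A reader might infer that the plan cannot show mania at all, or that its detection rests on unprompted reports; the documents support neither. None of these outputs, however, gives a prespecified YMRS case count by arm.

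Second, nothing in the SAP says that withdrawn patients are deleted. The Efficacy Set needs only one post-dose score, and the intention-to-treat wording keeps everyone randomised. This stands too: omission is an inference from the method described and the absence of imputation, and the SAP does not reconcile the two. The same gap affects every scale, MADRS included, so it is not peculiar to YMRS. The YMRS point does not depend on it, because the mean comparison is weak even with all patients kept.

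Third, the documents give no baseline YMRS and no entry limit on it, so a floor at baseline is plausible but not shown. Finally, a table of counts will not settle the question inferentially with 20 per arm. That is correct, and it is why the table should be descriptive.

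**Conclusion.** The point holds as a modest improvement to reporting. YMRS is classed as efficacy, and its only planned group comparison is likely to miss emergent mania, so a flat mean is not evidence of absence. On the assumed inputs, 1 to 3 cases among 20 would make the mean comparison significant in about 2–20% of trials if the patients are kept, and only at the chance rate of about 5% if they are omitted. These figures rest on an assumed SD, correlation, size and timing of the rise, and number of cases; the direction follows from the arithmetic of a mean over 20 patients.

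It would go too far to conclude that the plan hides mania or prescribes dropping these patients. Other planned outputs could show it, and the population definitions nominally retain them. The primary endpoint and the sample size are unaffected.

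**What to change.** 1. Move YMRS from the secondary efficacy lists (protocol; SAP 3.1.2) to the safety measures (protocol Safety Index; SAP 3.2), and add a YMRS subsection to SAP 5.5.
2. In the Safety Set, report descriptively by arm the highest post-baseline YMRS score and the number of patients above a cut-off that the sponsor fixes before unblinding. Use every score recorded up to withdrawal.
3. Keep mean change from baseline as description only, and state how withdrawn patients enter that summary.

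The cost is revised wording in two documents, a prespecified cut-off and one table from scores already scheduled. The table partly overlaps the adverse event summaries and has little inferential power at 20 per arm. A YMRS score at withdrawal would make the peak more complete, but it is additional data collection and the fix does not need it.
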